## **PURPOSE SAP**

### **Protocol # B1801035**

- Incidence of cancer in-situ, and SIR (95% CI) if appropriate population-based rates for cancer in-situ are available (secondary analysis)

In addition, narrative summaries for any malignancies reported, based on data captured in the Registry database, additional information provided to the Endpoint Adjudication Panel such as pathology reports and data received from Pfizer drug safety will be included as part of the analysis.

### **7.5 *Other serious adverse events associated with exposure***

A patient listing of all SAEs will be generated, including verbatim term and MedDRA SOC and PT, onset date, total cumulative exposure at time of onset, date of last dose of etanercept prior to onset, date of first dose of etanercept and calculated interval between last dose and onset in days [if precision of event dates allow, otherwise use response to question whether within 28 days (yes, no, unknown)].

The following summaries will also be presented:

- Number of unique patients, total number of events, and incidence rate of all reported SAEs (by MedDRA SOC and PT)
  - Including serious and opportunistic infections and excluding malignancies
  - Excluding serious and opportunistic infections and malignancies
  - By treatment period (initial 24 weeks/ post 24 weeks/all follow-up)

Summary of SAE distribution [mean # of events reported per patient (SD), median, range]

Summary of serious TEAE will also be provided as per basic results disclosure (Pfizer standard).

The events described will be identified based on serious yes/no variable reported as Yes and onset date greater or equal to the first administration of Enbrel reported in the study. Serious events with missing onset date will be also included.

### **7.6 *Other adverse events associated with exposure***

The following Pfizer standard summaries will also be presented:

- Discontinuation due to AE
- TEAE (all causality and related)
- TEAE by severity (all causality and related)
- TEAE by severity and relationship

Summary of both serious and non-serious TEAE (all causality) and summary of non-serious TEAE with frequency  $\geq 5\%$  (all causality) will also be provided as per basic results disclosure (Pfizer standard).

## **PURPOSE SAP**

**Protocol # B1801035**

A patient listing of all non-serious AEs and all AEs reported as possibly related to etanercept will be generated, including verbatim term and MedDRA SOC and PT, onset date, total cumulative exposure at time of onset, date of last dose of etanercept prior to onset, date of first dose of etanercept and calculated interval between last dose and onset in days [if precision of event dates allows, otherwise use response to question whether within 28 days (yes, no, unknown)].

Summaries of number of unique patients and total number of events of all reported non-serious AEs (by MedDRA SOC and PT) will also be presented.

### **7.7 Effectiveness of treatment**

Treatment discontinuation for lack of desired therapeutic effect will, for purposes of analysis, serve as a proxy for treatment effectiveness.

A listing will be generated presenting all patients discontinuing the initial course of etanercept which will include reason for discontinuation, duration of initial course and use of previous systemic therapies.

The following summaries will also be presented:

- Summary of proportion of patients who discontinue etanercept early (< 24 weeks) due to lack of effect, AE or intolerance (primary analysis) during any period of etanercept treatment
- Summary of treatment discontinuation among all patients during any period of etanercept treatment, by each reason and in aggregate (primary analysis)
- Summary of baseline characteristics, stratified by completion/non-completion of initial 24 weeks of therapy (primary analysis)
- Summary of proportion of patients who discontinue at > 24 weeks during any period of etanercept treatment due to lack of effect, AE or intolerance (secondary analysis)
- Summary of proportion of patients who have decreased disease severity after treatment with etanercept during any period of etanercept treatment compared to baseline (as a secondary analysis) stratified by completion of initial 24 weeks.

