11.5. Reporting to the EMA42
12. REFERENCES43

LIST OF TABLES

Table 0-1: Registry Flowchart6
Table 2-1: Opportunistic Infections11

LIST OF ABBREVIATIONS

ADR	adverse drug reaction
AE	adverse event
CHMP	Committee for Medicinal Products for Human Use
CRF	case report form
DMARDs	disease-modifying anti-rheumatic drugs
DSU	Drug Safety Unit
EC	Endpoint Committee
EDC	electronic data capture
EIU	exposure in-utero
EMA	European Medicines Agency
EU	European Union
FDA	US Food and Drug Administration
GPP	Good Pharmacoepidemiology Practices
ICF	informed consent form
ICH	International Committee on Harmonisation
IEC	independent ethics committee
ISPE	International Society for Pharmacoepidemiology
JC virus	John Cunningham virus
JIA	juvenile idiopathic arthritis
MedDRA	Medical Dictionary for Regulatory Activities
NICE	National Institute for Health and Clinical Excellence
NRP	national responsible person
PASS	post-authorisation safety study
PSUR	periodic safety update report
PUVA	psoralen ultraviolet A phototherapy
RA	rheumatoid arthritis
RMF	registry master file
RP	registry physician
RSF	registry site file
SAE	serious adverse event
SAP	statistical analysis plan
SIR	standardized incidence ratio
SSC	Scientific Steering Committee
TB	tuberculosis
TNF	tumour necrosis factor
UV	ultraviolet

Table 0-1: Registry Flowchart

Study Interval	Data Collected		
	Enrolment	Year 1 – Year 2	Year 3 – Year 5 ^a
	Baseline	Every 3 months (± 4 weeks)	Every 6 months (± 4 weeks)
Visit ID	1	2 – 8	9 – 12
Informed consent/assent	X		
Patient/legal representative contact information	X	X	X
Demographics	X		
Medical history	X		
Co-morbidities	X	X	X
Psoriasis history (including date of diagnosis, severity assessment, previous treatments)	X		
Etanercept exposure	X ^b	X	X
Treatment discontinuation		X	X
Other systemic psoriatic treatments ^b	X	X	X
Prior medications	X		
Concomitant medications	X	X	X
Serious and pre-specified opportunistic infections ^c	X ^b	X	X
Malignancies ^c	X	X	X
Other adverse events ^c		X	X
Registry discontinuation ^d	0	-----	X

- Patients enrolled after September 2013 may be followed for less than 5 years (i.e., until overall study completion in 2018)
- For patients being treated with etanercept prior to enrolment, details regarding etanercept dose and regimen, other systemic treatments, and serious and pre-specified opportunistic infections occurring since the first etanercept dose but before enrolment will be collected via retrospective medical record abstraction.

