### **5.3 Definition and measurement of exposure/risk windows**

#### **5.3.1 Etanercept**

##### **TREATMENT PERIODS (INITIAL AND SUBSEQUENT)**

It is anticipated that the etanercept treatment status for each patient will change throughout follow-up. A standard course of etanercept treatment is expected to last up to 24 weeks. Patients successfully responding to the first etanercept treatment course may be exposed to subsequent treatment (i.e., when patients experience a disease flare) and time window between 2 (or more) consecutive courses of treatment may vary substantially.

For the initial course of etanercept, whether the patient completed 24 weeks of treatment is recorded (yes/no), and if no, the number of weeks of treatment will be reported. Completion of initial 24 weeks of etanercept is defined as starting the first dose of etanercept within 30 day before the enrolment date or any time after enrolment date, and continuing for at least 168 days.

For each subsequent treatment period of etanercept, start and stop dates of treatment are collected. For all subsequent periods, the duration of treatment in weeks will be calculated. Cumulative exposure will be calculated by the sum, for each etanercept treatment period, of: [last dose date – first dose date] + 28. If there are less than 28 days between treatment periods, exposure will be considered uninterrupted (i.e., part of the same treatment period).

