## **6.2 Sample size**

No formal sample size calculation was performed in the design of the Registry since the goal is to obtain participation by all eligible patients. It should also be noted the study is descriptive only (i.e., non-comparative) and therefore not designed to assess differences amongst etanercept users or users of other therapies. Current available data are insufficient to project population-based estimates of paediatric patients with severe psoriasis treated with conventional systemic therapy who were not well-controlled and would warrant further intervention such as that potentially afforded by etanercept.

The best research estimates suggest that during the first 3 years following market authorization for treatment of severe disease in patients aged 8 through 17, approximately 250 patients will be treated with etanercept throughout Europe. Long-term follow-up studies, with a young and potentially highly mobile population and widely-spaced follow-up timepoints (Years 3 – 5), may incur a higher rate of loss-to-follow-up. The Registry will target 100 to 200 patients.

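### The primary discontinuation summaries have no stated unit, time horizon or censoring rule, so they move with follow-up, number of courses and prevalent users as well as with the stopping rate

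*SAP*

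**What the plan says.** SAP 7.7 states the role of the measure: "Treatment discontinuation for lack of desired therapeutic effect will, for purposes of analysis, serve as a proxy for treatment effectiveness". It then labels three summaries as primary.

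- Early stopping: "proportion of patients who discontinue etanercept early (< 24 weeks) due to lack of effect, AE or intolerance (primary analysis) during any period" of treatment.
- Stopping in general: "Summary of treatment discontinuation among all patients during any period of etanercept treatment, by each reason and in aggregate (primary analysis".
- A baseline table: "Summary of baseline characteristics, stratified by completion/non-completion of initial 24 weeks of therapy (primary analysis".

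A secondary summary covers stops after 24 weeks, again over any treatment period. None of the three discontinuation summaries comes with a time horizon, a per-course or person-time denominator, or a censoring rule. The patient-year rates defined in SAP 6.6 are applied to safety events only.

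Four features of the design bear on these summaries.

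- **Length of follow-up.** The footnote to Protocol Table 0-1 says "Patients enrolled after September 2013 may be followed for less than 5 years".
- **Dropout.** SAP 6.2 warns that long follow-up in a young, mobile population "may incur a higher rate of loss-to-follow-up". It gives no rate.
- **Courses.** SAP 5.3.1 expects repeat courses and says the "time window between 2 (or more) consecutive courses of treatment may vary substantially". SAP 5.2.5 adds that some patients may be treated continuously beyond 24 weeks.
- **Prevalent users.** Protocol 4.2 admits patients already on etanercept, however long they have been treated.

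**The concern.** A proportion of patients who stop over all periods has a clear meaning only if everyone is observed for the same time and over the same number of courses. Neither holds here. Someone with four courses has four opportunities to stop early, and someone with one course has one. A patient followed for five years has longer in which to stop than one followed for three. A patient who enters after week 24 of the initial course can no longer stop that course early, yet may sit in the denominator.

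SAP 7 rests interpretation on point estimates and 95% confidence intervals. The estimate that stands in for effectiveness therefore needs a defined unit and time scale. Without them, two readers could compute different figures from the same data, and neither figure could be read as a stopping risk.

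**Working it through.** **Inputs from the documents.** The plan gives no discontinuation rate, dropout rate, distribution of courses or precision target for effectiveness, so it has no figure of its own to reproduce. Protocol 3 and SAP 4 plan 60 to 80 patients (SAP 6.2 still carries 100 to 200). Protocol 5 starts enrolment in Q4 2010, runs it for about 4 to 5 years, and ends follow-up in 2018. The last patients would thus enter between Q4 2014 and Q4 2015 and have at most about 3 to 4 years, against 5 for early entrants.

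**Assumed inputs.** Early-stop risk per course *p*, stopping hazard *h*, number of courses *k*, and share *r* of patients entering past week 24.

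**1. Number of courses.** With independent courses and constant *p*, P(at least one early stop) = 1 − (1 − *p*)^*k*.

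| *p* | *k* = 1 | *k* = 2 | *k* = 3 | *k* = 4 |
|---|---|---|---|---|
| 10% | 10.0% | 19.0% | 27.1% | 34.4% |
| 20% | 20.0% | 36.0% | 48.8% | 59.0% |

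For *p* = 15%: 1 − 0.85 = 15%, 1 − 0.85² = 28%, 1 − 0.85⁴ = 48%.

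For a mixed cohort (half with one course, 30% with two, 20% with three) and *p* = 20%: 0.5 × 20.0 + 0.3 × 36.0 + 0.2 × 48.8 = 30.6%.

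In reverse, an observed 27.1% fits *p* = 27.1%, 14.6%, 10.0% or 7.6% for 1, 2, 3 or 4 courses each.

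**2. Length of follow-up.** With continuous treatment and constant *h*, P(stopped by *t*) = 1 − exp(−*ht*). For *h* = 0.2 per year, 1 − exp(−0.6) = 45.1% at 3 years and 1 − exp(−1.0) = 63.2% at 5 years, a ratio of 1.40. The ratio is 1.52 at *h* = 0.1 and 1.24 at *h* = 0.4.

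**3. Prevalent users.** If a share *r* enters past week 24 and stays in the denominator, initial-course early stopping reads *p*(1 − *r*). With *p* = 20%, that is 15% for *r* = 25% and 10% for *r* = 50%.

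**4. Which summary is affected by what.** The early-stopping summary has a fixed window of under 24 weeks within each course, so steps 1 and 3 matter most and follow-up acts mainly through the number of courses. The by-reason and after-24-week summaries have no such window, so step 2 applies to them as well.

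**5. Sampling error for scale.** The 95% half-width at 20% is 1.96 × √(0.2 × 0.8 / *N*): 10.1 points at *N* = 60 and 8.8 points at *N* = 80.

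**The case against.** The strongest reply is that the registry is descriptive. Protocol 2.1.2 says effectiveness is not measured directly, SAP 6.2 calls the study non-comparative, and SAP 7 plans no hypothesis test. Related information is already planned: a listing of initial-course stops with reason and duration (SAP 7.7), treatment duration in prospective patients and counts of complete and incomplete periods (SAP 7.2), and follow-up time (SAP 9.2). Table shells exist according to the SAP document history. They are not among the documents reviewed and may fix the denominators.

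The arithmetic can also be challenged. Protocol 7.4 and SAP 5.3.1 describe re-treatment of patients who responded to the first course, so later courses are not independent draws at the same risk, and the 48% at four courses is probably too high. The hazard illustration assumes continuous treatment, while the course illustration assumes discrete courses. Protocol 4.3 excludes patients judged unlikely to complete two years, so the 2018 cut-off hardly touches first-course stopping before week 24.

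These points stand as limits on size and consequence: no test or error rate is affected, and the percentages are illustrations. They do not supply the missing definition. The listing and the counts are ingredients, and none of them is a by-reason estimate that handles incomplete follow-up. Protocol 7.4 planned stratification of discontinuation by cumulative dose, duration and pattern of use, but the nearest SAP counterpart is an optional exploratory analysis by cumulative exposure (SAP 8). If the shells do settle the unit and denominator, the SAP text should say so.

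**Conclusion.** The point holds for two of the three primary summaries and for the secondary summary of stops after 24 weeks. The primary baseline table is not affected. As written, the crude proportions depend on follow-up, number of courses and the share of prevalent users in addition to the stopping rate. Under the assumed rates, the shift can exceed the sampling half-width of 9 to 10 points: 13 points between one and two courses at 15% per course (15% to 28%), and 18 points between three and five years at 0.2 per year (45% to 63%). The first is probably an upper range.

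Three stronger inferences are tempting and are not supported.

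- *The figures reflect follow-up instead of the drug.* They reflect both: with three courses, *p* = 5% gives 14.3% and *p* = 20% gives 48.8%.
- *A patient lost or cut off on treatment is counted as not having stopped.* The SAP does not say this. The by-reason summary does not even state whether it counts patients or periods, and Protocol 6.2.2 records exposure as ongoing, completed or discontinued, so ongoing patients could be shown separately.
- *The estimate is biased in a known direction.* Incomplete follow-up and prevalent users would pull it down and repeat courses would push it up. The documents do not allow a net direction.

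Safety is the registry's main focus and is untouched. This is a cheap improvement to the effectiveness proxy.

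**What to change.** 1. State for each discontinuation summary in SAP 7.7 whether the unit is the patient or the course, and give its denominator.
2. For the initial course in prospective patients as defined in SAP 6.5, report cumulative incidence of discontinuation by reason (lack of effect; AE or intolerance; clearing; other), treated as competing reasons. Censor at last contact and give estimates with 95% CI at week 24 and one or two later times. The SAP 6.5 definition includes starts up to 30 days before enrolment, so count time from first dose with entry at enrolment for those patients.
3. Include prevalent users only with delayed entry, or show them separately. Otherwise their guaranteed time on treatment before entry biases the first-course estimate low.
4. Report later courses per course and by course number.
5. Carry the Protocol 7.4 stratification by duration and pattern of use into the SAP where numbers allow, and keep the crude counts as supportive.

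The data are largely in hand: first-dose date (Protocol 6.2.1), exposure status and reason (Protocol 6.2.2), weeks or dates of treatment (SAP 5.3.1) and last-dose date in the duration formula (SAP 6.6). SAP 5.3.1 describes weeks for an incomplete initial course and dates for later periods, so the precision of initial-course dates should be checked first. The cost is a few more tables, and by-reason estimates will be sparse with 60 to 80 patients. SAP version 5.0 is dated February 2019, after the planned 2018 end of follow-up, so analyses added once data have been seen should be labelled as added.

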4.2. Inclusion Criteria

To be eligible for registry enrolment, patients must meet all of the following criteria:

- Age ≤ 17 years at time of administration of the first dose of etanercept
- Diagnosis of plaque psoriasis by a dermatologist
- Prior to enrolment, a clinical decision has been made to prescribe etanercept for the treatment of psoriasis
- Newly prescribed with initial etanercept or actively being treated with etanercept, regardless of length of treatment prior to study enrolment
- Capable and willing to provide paediatric assent, or written informed consent when applicable, and
- Parent(s)/legal representative of patient is capable and willing to provide written informed consent

- Evidence of a personally signed and dated informed consent document indicating that the patient (or a legally acceptable representative) has been informed of all pertinent aspects of the study must exist.

Please note: Currently etanercept is approved for the treatment of severe plaque psoriasis in children and adolescents from the age of 6 years who are inadequately controlled by, or are intolerant to, other systemic therapies or phototherapies. The registry protocol will not encourage use of etanercept at younger ages. However if a doctor, in collaboration with the child's parents, makes the independent clinical decision to prescribe etanercept to a child less than 6 years of age for severe plaque psoriasis, that child may be included in the registry.

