6.2.1. Baseline Visit

During the enrolment visit, the site will be instructed to obtain additional information regarding the patient, including secondary contact information and contact information for the patient's primary health care provider.

The following information will be collected:

1. Date of informed consent(s)/assent
2. Patient/legal representative contact information, including secondary contacts and primary health care provider details, if different than RP
3. Demography [age, gender, weight, race/ethnicity (where allowed by local regulation)]
4. Medical history/co-morbid medical conditions
5. Plaque psoriasis history
 - a. Physician's global subjective assessment of disease severity (four-point scale)
 - b. Prior treatments or therapies, including topical agents and immunosuppressive therapies and the patient's response to each.
6. Etanercept Treatment
 - a. Initial prescribed etanercept treatment regimen
 - b. Date of first dose
7. Concomitant medications, including immunosuppressants
8. Retrospective medical record abstraction for patients with historical treatment with etanercept will also include:
 - a. Etanercept dosing history
 - b. Use of additional systemic therapies since starting etanercept
 - c. Occurrence of serious and/or pre-specified opportunistic infections and SAEs

Note: Due to the significance of the AEs of interest (serious and opportunistic infections and malignancies), it is considered highly likely that these events, if they occurred, would be documented in the medical record of the prescribing RP. Retrospective data for other SAEs overall, however, may not be consistently recorded; therefore, all retrospective SAEs will be collected but analysed separately.

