6.2.2. Follow-up Visit

FOLLOW-UP: YEAR 1 THROUGH 2

Regardless of the duration of etanercept exposure at the time of registry enrolment, all patients will be followed prospectively using the same schedule. During follow-up, the RP or other trained site staff will collect data during routine clinical visits. Routine clinical visits may not coincide with registry timepoints; therefore alternatively, the RP, trained site staff or CRO registry staff may administer follow-up questionnaires via phone interviews.

The following data will be collected every 3 months (\pm 4 weeks) during the first 2 years of participation:

1. Updated informed consent information (e.g., if patient turns 18 since last follow-up)
2. Updated contact information
3. Status of etanercept exposure (ongoing/completed/discontinued/reason for discontinuation)
4. Requirement for additional psoriasis treatment
 - a. Continued etanercept
 - b. Other systemic treatments
 - c. Use of topical agents
 - d. Reason for treatment decision
5. Physician's global subjective assessment of plaque psoriasis severity
6. Changes in medical status, including new onset comorbid medical conditions
7. Changes/additions to concomitant medications
8. AEs as described in [Section 2.1.1](#), Safety Endpoints
 - a. Serious and pre-specified opportunistic infections
 - b. Malignancies
 - c. Other AEs

FOLLOW-UP: YEAR 3 THROUGH YEAR 5/END OF FOLLOW-UP

The following data will be collected every 6 months (\pm 4 weeks) during year 3 through the end of participation:

1. Updated informed consent information (e.g., if patient turns 18 since last follow-up)

2. Updated contact information
3. Status of etanercept exposure (ongoing/completed/discontinued/reason for discontinuation)
4. Requirement for additional psoriasis treatment
 - a. Continued etanercept
 - b. Other systemic treatments
 - c. Use of topical agents
 - d. Reason for treatment decision
5. Physician's global subjective assessment of plaque psoriasis severity
6. Changes in medical status, including new onset comorbid medical conditions
7. Changes/additions to concomitant medications
8. AEs as described in [Section 2.1.1](#), Safety Endpoints
 - a. Serious or pre-specified opportunistic infections
 - b. Malignancies
 - c. Other AEs

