## **5. Variables Used for Analysis**

### **5.1 Data Sources**

Data will be collected from treating physicians, who will provide information on current medications and status of the Registry patients at enrolment and at each suggested follow-up assessment.

Following enrolment in the registry, the physician will also provide information by retrieving medical record information at his/her own institution and other health care settings, as appropriate. Data will be collected and recorded directly from the patient or their parent/guardian only if the patient has been lost to follow-up by the physician. If any of the outcomes of interest are reported directly by patients or their parents/guardians, additional attempts to collect supporting information from treating physicians will be made. In order to provide complete narratives for interim and final study reports, for any reported malignancies, any additional information provided via NIS SAE Form AEM01 and other follow-up reports to Pfizer's drug safety department or the Endpoint Adjudication Panel will be used to augment the data collected in the CRF.

Baseline data are expected to be recorded at the time of enrolment to this registry. Follow-up data are to be collected every 3 months ( $\pm$  4 weeks) during the first 2 years, and every 6 months ( $\pm$  4 weeks) during Year 3 through Year 5 of participation, either at the time of routine clinical visits, or alternatively via telephone interview.

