#### **5.2.5 Effectiveness**

To the extent possible effectiveness (or lack of effectiveness) will be inferred from patterns of treatment and re-treatment. The recommended course of etanercept treatment for paediatric psoriasis is for up to 24 weeks; physicians should consider discontinuation of etanercept if a satisfactory response is not achieved by 12 weeks.

The following data will be used to evaluate effectiveness:

- Whether a patient receives initial course of etanercept for less than 24 weeks and reason for discontinuation is not recorded as "clearing of psoriasis"
- Whether a patient is required subsequent treatment periods of etanercept or other systemic therapies after completion of initial course
- Whether a patient receives subsequent treatment periods of etanercept for less than 24 weeks
- Whether a patient has decreased disease severity after treatment with etanercept compared to baseline

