### **5.4 Definition and measurement of covariates**

A critical element of understanding the potential association of adverse outcomes with etanercept product exposure is the inclusion of appropriate covariates in the analyses. In order to better characterize the patients who experience or do not experience the events of interest, the following additional patient characteristics and exposures with the potential to affect clinical outcomes or interpretation of the data are collected at baseline:

Demography:

- Age
- Gender
- Race/ethnicity

Related to plaque psoriasis:

- Duration of disease at baseline
- Severity of plaque psoriasis (none, mild, moderate, severe)
- Diagnosis of psoriatic arthritis
- Previous (or current) use of common plaque psoriasis therapies (topical or systemic)
- Response to previous or current therapies (none, poor, fair, good, excellent/complete, unknown)

Other covariates:

- Medical history and co-morbid conditions
- Other concomitant medications

Current plaque psoriasis disease severity, co-morbidities and all medication exposures are also collected/updated at each follow-up time point.

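### SAP 7.7's severity-improvement proportion uses an on-treatment baseline in retrospective patients and gives no rule for choosing among repeated ratings

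*SAP*

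**What the plan says.** SAP 5.2.5 lists among the effectiveness data "Whether a patient has decreased disease severity after treatment with etanercept compared to baseline". SAP 7.7 turns this into a "Summary of proportion of patients who have decreased disease severity after treatment with etanercept during any period of etanercept treatment compared to baseline"; the bullet goes on to label it secondary and to stratify it by completion of the initial 24 weeks. Neither section names a visit, a window, a choice among several ratings, a rule for patients already at the lowest grade, or a rule for missing ratings.

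The rating is the physician's subjective global assessment in four grades, none to severe (Protocol 6.2.1, SAP 5.4). It is repeated: "Current plaque psoriasis disease severity, co-morbidities and all medication exposures are also collected/updated at each follow-up time point" (SAP 5.4; likewise Protocol 6.2.2).

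On the baseline, SAP 5.1 says "Baseline data are expected to be recorded at the time of enrolment to this registry". Protocol 4.2 admits patients newly prescribed etanercept and also those "actively being treated with etanercept, regardless of length of treatment prior to study enrolment". SAP 6.5 calls patients prospective if they started no more than 30 days before enrolment or at any time after it, and the others retrospective. For patients already on treatment, the items abstracted from before enrolment are dosing, other systemic therapy, infections and SAEs (Protocol Table 0-1 and 6.2.1). Severity before the first dose is not listed.

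SAP 7 bases tables on the total registry population unless a section says otherwise. SAP 7.2 names prospective patients for its exposure tables; SAP 7.7 does not.

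**The concern.** Two features of the definition affect the percentage, and they can pull in opposite directions.

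First, a retrospective patient who responded before enrolment enters with an already lowered rating, possibly at the floor of the scale. Under the plan this patient counts as not improved. Because the completion rule in SAP 5.3.1 requires a start within 30 days before enrolment or later, the patient cannot be a completer either, and lands in the no or unknown stratum beside patients who stopped early.

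Second, without a rule for choosing the rating, two programmers could follow the text and report quite different figures. If any lower rating in any course counts, the proportion rises with the number of ratings even when disease is stable. Protocol 1 describes psoriasis as remitting and relapsing, so some fluctuation without a drug effect is to be expected.

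What is at stake is the one effectiveness summary that uses a disease rating; the others infer effect from treatment patterns.

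**Working it through.** The documents give no figure for this summary, so there is nothing to reproduce. The sums below show direction and rough size.

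**1. Dilution by the on-treatment baseline**

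Let q be the true proportion improved since before treatment, s the retrospective share, and c the share of retrospective improvers whose improvement came before enrolment.

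Observed proportion = (1 − s)q + s·q·(1 − c) = q(1 − s·c).

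Inputs:
- q = 57%, the week-12 response in the randomised trial described in Protocol 1.1. It is on a different scale and serves only as an anchor.
- s = 10% to 50%, assumed. Protocol 6.2 expects the group to be limited and gives no number.
- c = 50% to 100%, assumed.

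| s | c = 50% | c = 75% | c = 100% |
|---|---|---|---|
| 10% | 54% | 53% | 51% |
| 25% | 50% | 46% | 43% |
| 50% | 43% | 36% | 28.5% |

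The loss is 57·s·c percentage points, from about 3 (57 × 0.10 × 0.50) to 28.5 (57 × 0.50 × 1). For scale, the exact 95% interval around 57% is about 43% to 69% with 60 patients and 46% to 68% with 80.

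**2. Where these patients fall in the strata**

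- Completer: needs a start no more than 30 days before enrolment, so no retrospective patient qualifies. This stratum is clean apart from prospective patients with up to 30 days of etanercept before the baseline rating.
- No or unknown: true early stoppers mixed with retrospective patients, who are by selection still on treatment. The mixture shifts this proportion in a direction that depends on how the two groups compare, which the documents do not tell us.

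**3. Chance improvement if any lower rating counts**

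With probability p of a chance lower rating at each visit, no true change and independent visits, the chance of at least one in n visits is 1 − (1 − p)^n.

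Inputs: p is assumed. For n, one 24-week course has about 2 three-monthly ratings. Five years have 24/3 + 36/6 = 14 by the stated schedule, or 11 by the visit numbers in Protocol Table 0-1.

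| p | n = 1 | n = 2 | n = 5 | n = 14 |
|---|---|---|---|---|
| 5% | 5% | 10% | 23% | 51% |
| 10% | 10% | 19% | 41% | 77% |
| 20% | 20% | 36% | 67% | 96% |

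For p = 10%: 1 − 0.9² = 0.19; 1 − 0.9⁵ = 0.41; 1 − 0.9¹⁴ = 0.77.

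Ratings on one patient are correlated, so independence gives an upper bound. In a simulation of stable disease on a four-grade scale (baseline moderate or severe, within-patient correlation 0.8, autocorrelation of the fluctuation 0.5), at least one lower rating occurred in 27% over 2 visits and 63% over 14, against 24% at visit 14 alone. With correlations from 0.6 to 0.95 and autocorrelations from 0 to 0.8, any-of-14 ran from 27% to 84%, and a single late visit from about 12% to 33%. Fixing one rating removes the growth with follow-up, not all chance improvement.

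**The case against.** The case for leaving the text alone has four parts.

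- **The analysis is minor.** It is secondary, descriptive and without hypothesis tests. SAP 4 makes it conditional on severity data for most patients. Protocol 2.1.2 says effectiveness is not measured directly and takes discontinuation for lack of effect as the proxy. This stands, and it limits the importance of the point.
- **The planned stratification protects one stratum.** Completers exclude retrospective patients by definition. This stands. A reader might infer that the reported percentage cannot be interpreted at all; the documents do not support that, because the completer stratum is largely sound and the retrospective group is expected to be limited.
- **The SAP does not prescribe an ever-improved rule.** A reader might infer that one lower rating at any of 14 visits counts and that later worsening never undoes it. The text does not say so. SAP 5.3.1 and 6.6 use period for a treatment course, and other bullets in 7.7 use the same phrase about discontinuation, where it means courses. Counting any visit is one possible reading. Fourteen on-treatment ratings would need some five years of near-continuous use, which SAP 5.2.5 allows for but which is the extreme. What stands against the plan is that no rule is given for choosing within or across courses.
- **The shells may already split the table.** The SAP document history mentions a retrospective column in some shells, and SAP 6.5 lists enrolment type as a subgroup where specified. The shells are not in the documents, and 7.7 does not specify the split, so this cannot be relied on.

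**Conclusion.** The baseline problem holds on the text: following the plan as written counts patients who improved before enrolment as not improved, dilutes the overall proportion, and mixes these patients with early stoppers in the no and unknown strata. The missing selection rule is a real gap, but an ambiguity rather than a demonstrated inflation.

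The sizes are illustrative. Dilution from 57% to somewhere between 54% and 28.5% depends on the assumed retrospective share and the assumed timing of their improvement. Chance improvement of 19% over 2 visits, 41% over 5 and 77% over 14, against 10% at one visit, assumes a 10% rate per visit, independence and an any-rating rule; 77% is an upper bound. The documents give neither the fluctuation rate nor the retrospective share.

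This is a cheap improvement. It affects how a secondary effectiveness summary can be read and leaves the safety objectives untouched.

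**What to change.** Amend SAP 5.2.5 and 7.7 as follows.

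1. Present the summary by enrolment type. Base the improvement proportion on prospective patients only. Show retrospective patients separately as change since enrolment, with no claim of improvement from treatment. Flag prospective patients whose baseline rating came after the first dose, or repeat the summary without them; up to 30 days of prior treatment is possible in this group.
2. Use one rating per patient for the first course: the one closest to week 24 after the first dose. The window must suit a schedule that runs from enrolment. A patient who started 30 days before enrolment has visits near treatment weeks 13 + 4.3 ≈ 17 and 26 + 4.3 ≈ 30, so ±4 weeks would miss both. With 13 weeks between visits, the nearest scheduled one is at most 6.5 weeks away, so ±7 weeks is reasonable. For patients who stopped earlier, use the last rating on that course and keep them in the denominator; dropping them would bias the proportion upward.
3. Show the result as a baseline-by-follow-up shift table, with the number of missing ratings and the number already at the lowest grade at baseline.

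The data are already collected. The cost is SAP wording, a little more programming and a smaller denominator for the improvement proportion.
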